#### 4.3.2 Randomization/Subject Registration

For participants from whom informed consent has been obtained, but who are deemed ineligible or who do not enroll into the initial protocol step, an ACTG Screening Failure Results form must be completed and keyed into the database.

#### 4.4 Coenrollment Guidelines

Sites are encouraged to coenroll participants in A5243, "Plan for Obtaining Human Biological Samples at Non-US Clinical Research Sites for Currently Unspecified Genetic Analyses." Coenrollment in A5243 does not require permission from the A5290 protocol chairs. For specific questions and approval for coenrollment in other studies, sites must contact the protocol chairs via e-mail as described in the Study Management section.

### 5.0 STUDY TREATMENT

#### 5.1 Regimens, Administration, and Duration

##### 5.1.1 For Participants Enrolled During Accrual Period 1

At entry, participants will be randomized (1:1:1) to one of the following three arms: Arm A, Arm B, and Arm C as further defined in this section. Anti-TB therapy with study-provided RBT or non-study-provided RIF and non-study-provided INH, EMB, and PZA should be started within 72 hours of randomization. ART should be started as soon as possible after initiating anti-TB therapy, but may be delayed for up to 7-14 days after initiation of anti-TB therapy to allow for assessment of initial tolerability of TB medications.

###### 5.1.1.1 Arm A

###### ART

###### Entry through Week 72

- LPV 400 mg/ RTV 100 mg orally twice daily plus 2 NRTIs
- After completion of TB treatment, ART will continue at initial dosing through week 72: LPV 400 mg/ RTV 100 mg orally twice daily plus 2 NRTIs

###### Anti-TB Therapy

Participants will receive the following anti-TB medications with recommended dosing, unless dose adjustments are required (see Table 5.1):

###### Entry through Week 8 study visit (or until completion of intensive TB treatment as determined after dose adjustment in accrual period 1 participants)

- INH 300 mg orally once daily
- RBT 300 mg orally once daily, then 150 mg orally once daily upon initiation of ART\*
- EMB (15 to 20 mg/kg) orally once daily
- PZA (20 to 30 mg/kg) orally once daily (not to exceed 2 g per day)
- Pyridoxine 25 mg orally once daily

Week 8 study visit through Week 24 (or as determined by primary clinician if longer anti-TB treatment required)

- INH 300 mg orally once daily
- RBT 150 mg orally once daily
- Pyridoxine 25 mg orally once daily
- INH, RBT, and pyridoxine will continue through week 24 for a minimum total duration of 24 weeks

INH, RBT, and pyridoxine may continue beyond 24 weeks to a maximum of 48 weeks at the discretion of the primary clinician, and the protocol core team must be notified.

#### 5.1.1.2 Arm B

##### ART

Entry through Week 72

- LPV 800 mg/ RTV 200 mg orally twice daily plus 2 NRTIs, unless dose adjustments are required (see Table 5.1)
- After completion of TB treatment, ART will change to standard dosing (LPV 400 mg/RTV 100 mg orally twice daily plus 2 NRTIs) through week 72

##### Anti-TB Therapy

Participants will receive the following anti-TB medications with recommended dosing:

Entry through Week 8 study visit (or until completion of intensive TB treatment as determined after dose adjustment in accrual period 1 participants)

- INH 300 mg orally once daily
- RIF (weight-based dose; for weight < 45 kg: 450 mg orally once daily; for weight  $\geq$  45 kg: 600 mg orally once daily) orally once daily
- EMB (15 to 20 mg/kg) orally once daily
- PZA (20 to 30 mg/kg) orally once daily (not to exceed 2 g per day)
- Pyridoxine 25 mg orally once daily

Week 8 study visit through Week 24 (or as determined by primary clinician if longer anti-TB treatment required)

- INH 300 mg orally once daily
- RIF (weight-based dose; for weight < 45 kg: 450 mg orally once daily; for weight  $\geq$  45 kg: 600 mg orally once daily) orally once daily
- Pyridoxine 25 mg orally once daily
- INH, RIF, and pyridoxine will continue through week 24 for a minimum total duration of 24 weeks

INH, RIF, and pyridoxine may continue beyond 24 weeks to a maximum of 48 weeks at the discretion of the primary clinician and the protocol core team must be notified.

#### 5.1.1.3 Arm C

##### ART

###### Entry through Week 72

- LPV 400 mg/ RTV 100 mg orally twice daily plus 2 NRTIs
- RAL 400 mg orally twice daily
- After completion of TB treatment, ART will continue at initial entry dosing through week 72: LPV 400 mg/ RTV 100 mg orally twice daily plus 2 NRTIs and RAL 400 mg orally twice daily

##### Anti-TB Therapy

Participants will receive the following anti-TB medications with recommended dosing, unless dose adjustments are required (see Table 5.1):

###### Entry through Week 8 study visit (or until completion of intensive TB treatment as determined after dose adjustment in accrual period 1 participants)

- INH 300 mg orally once daily
- RBT 300 mg orally once daily, then 150 mg orally once daily upon initiation of ART\*
- EMB (15 to 20 mg/kg) orally once daily
- PZA (20 to 30 mg/kg) orally once daily (not to exceed 2 g per day)
- Pyridoxine 25 mg orally once daily

###### Week 8 study visit through Week 24 (or as determined by primary clinician if longer anti-TB treatment required)

- INH 300 mg orally once daily
- RBT 150 mg orally once daily
- Pyridoxine 25 mg orally once daily
- INH, RBT, and pyridoxine will continue through week 24 for a minimum total duration of 24 weeks

INH, RBT, and pyridoxine may continue beyond 24 weeks to a maximum of 48 weeks at the discretion of the primary clinician, and the protocol core team must be notified.

\*NOTE: In Arms A and C, RBT should be administered at a dose of 300 mg daily until the start of antiretroviral therapy at which time the dose should be reduced to the 150 mg daily dose. All participants will receive TB treatment according to in-country TB guidelines for daily TB treatment and Directly Observed Therapy (DOT), except that all study participants will receive daily TB treatment 7 days

per week, i.e., participants will not use a 5 days per week schedule that may be recommended in some in-country TB programs.

If dose adjustments of LPV/r or RBT are deemed necessary, the intensive TB treatment phase will be extended at the adjusted dose for the relevant participants in the affected treatment arm, and participants will undergo additional drug level assessment (see detailed description in section 3.0).

Any participants determined to have clearly inadequate RBT concentrations during the accrual period 1 PK evaluation should be monitored closely after dose adjustments for TB outcomes throughout the course of their TB treatment.

If LPV/r is prematurely discontinued at any time during TB treatment, the team should be notified, and the RBT dose should be increased to 300 mg daily pending further instructions from the team.

Site pharmacists must receive new prescriptions from an authorized prescriber for dosing changes.

**NOTE:** A two accrual period design will be used as previously described. Because participants enrolled in the accrual period 1 will be undergoing treatment for active TB, they will continue on their randomized regimen pending the outcome of the accrual period 1 interim PK and safety evaluations. No participants will be enrolled in the accrual period 2 until completion of the accrual period 1 analysis and determination of subsequent dosing for LPV/r and RBT is made.

If, based on the SMC's determination, unacceptable PK or safety criteria are met within two treatment arms, then further enrollment into the study may be stopped, and the accrual period 1 participants will be managed according to best available local TB and antiretroviral treatment. These participants will be followed off study medication for the remainder of study follow-up (up to 72 weeks).

Table 5.1. LPV/r and RBT Dose Adjustment Table

	LPV/r Dose Adjustment	Rifabutin Dose Adjustment
Arm A	No dose adjustment	
RBT PK parameters low: Adjust RBT to RBT 300 mg orally three times weekly (TIW) or 300 mg orally once daily (see section 10.4).
 
RBT PK parameters high: Decrease RBT to RBT 150 mg orally TIW
 
NOTE: The RBT <math>C_{max}</math> will be used for the purpose of individual dose adjustment for low or high RBT concentrations. A low RBT concentration will be < 250 ng/mL. A high

		RBT $C_{max}$ will be greater than 900 ng/mL.
Arm B	
 
LPV <math>C_{min}</math> < 1 mg/L and <math>C_{max}</math> < 12 mg/L: add LPV 200 mg/RTV 50 mg (one additional fixed-dose combination tablet) twice daily
 
LPV <math>C_{min}</math> < 1 mg/L and <math>C_{max}</math> > 12 mg/L: add one additional RTV 100 mg tab tablet twice daily
 
 
NOTE: A LPV <math>C_{12}</math> (or trough) will be used to define whether an individual subject's LPV/r dose is too low.
	N/A
Arm C	No dose adjustment	
RBT PK parameters low: Adjust RBT to RBT 300 mg orally TIW or 300 mg orally once daily (see section 10.4).
 
RBT PK parameters high: Decrease RBT to RBT 150 mg orally TIW
 
NOTE: See Arm A for definition of RBT low and high concentrations.

Rifabutin Dose Adjustment:

RBT concentrations clearly associated with therapeutic success or an increased incidence of toxicity have not been established, although the range of 300-900 ng/mL for  $C_{max}$  has been associated with acceptable TB outcomes in a small number of patients. The RBT  $C_{max}$  will be used for the purpose of individual dose adjustment for low or high RBT concentrations. A low RBT  $C_{max}$  will be defined as < 250 ng/mL. This concentration represents the 25th percentile of RBT  $C_{max}$  values in 14 HIV and TB infected persons receiving a RBT dose of 150 mg once daily given in conjunction with LPV/RTV. A high RBT  $C_{max}$  will be greater than 900 ng/mL. This concentration is greater than 2 standard deviations in healthy volunteers receiving a 300 mg once daily RBT dose. The 300 mg RBT once daily dose is the usual RBT dose prior to an adjustment for the drug-drug interaction with LPV/RTV; a  $C_{max}$  > 900 ng/mL would represent an exposure above that usually seen in healthy volunteers or persons with TB.

LPV/r Dose Adjustment:

A LPV  $C_{12}$  (or trough) less than 1 mg/L will be used to define whether an individual participant's LPV/r dose is too low. A  $C_{12}$  value less than 1 mg/L is less than the 25th percentile of  $C_{12h}$  concentrations in a small study of HIV and TB infected persons receiving double dose LPV/RTV (i.e. 800/200 twice daily) with RIF, 600 mg once daily. A 12-hour post dose plasma concentration ( $C_{12h}$ ) value less than 1 mg/L is also considered the minimum threshold value for LPV by the DHHS Guidelines Panel. A  $C_{max}$  value > 12 mg/L is  $\geq$  the 75th percentile in HIV-infected persons receiving the usual twice daily 400/100 LPV/RTV dose.

NOTE: No substantive effect of RBT on LPV concentrations is expected based on prior PK data with this combination; however, if LPV levels in the ranges noted for Arm B are observed in Arm A or Arm C, then dose adjustments will be the same as for Arm B.

#### 5.1.2 For Participants Enrolled During Accrual Period 2

Once the accrual period 1 PK and safety analysis is completed and a determination is made to begin enrollment to accrual period 2, additional participants will be randomized into one of three treatment arms: Arm A, Arm B, and Arm C. Dosing for each treatment arm in accrual period 2 will be based on final dosing from the corresponding treatment arm during the dose-finding period in accrual period 1 participants.

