While the intent is to conduct the accrual period 1 PK and safety interim analysis after 54-60 accrual period 1 participants have completed 28 days of ART, available drug concentrations and safety data will be assessed weekly by the core team in an unblinded fashion as follows. Sites will be asked to batch PK samples and ship them every two weeks to the ACTG repository with immediate re-shipping to the PK laboratory. The PK laboratory will measure drug concentrations as soon as possible after receipt of shipments and will report results within 2 weeks of receiving the samples. The core team will monitor all available concentrations weekly for those results received to date. An early interim analysis of PK results and safety criteria will be evaluated after the first 10-12 participants in each treatment arm complete 28 days of ART and the day  $12 \pm 2$  drug concentrations are available to assess any early trends suggesting lower or higher than expected concentrations of any study-provided drug(s). (Please see the Study Monitoring Plan for more details on how this early PK assessment will be completed.) If the early assessments indicate concentrations out of acceptable ranges for more than three participants in a treatment arm or trends related to safety concerns, an early ACTG Study Monitoring Committee (SMC) evaluation will be triggered. Any dose adjustments recommended by the SMC in consultation with the core team after this interim evaluation will be implemented for any new accrual period 1 participants enrolled as soon as possible after the review and for any already enrolled participants who have drug concentrations clearly out of acceptable ranges. However, the decision to revise dose schedules and treatment duration of participants with inadequate drug concentrations would be made based not just on the drug concentrations, but also on all available clinical data regarding TB and HIV endpoints. While true real-time reporting of drug concentrations will not be possible, individual participants identified, either during weekly core team monitoring or during any early SMC monitoring assessments, who have clearly inadequate concentrations of any study-provided drug would be reported to the sites as soon as that determination is made, and individual dose adjustments may be recommended according to the dose adjustment schedule in Table 5.1 in section 5.1.1. Accrual period 1 participants for whom early dose adjustments are recommended will have drug concentrations repeated  $12 \pm 2$  days after initiating the adjusted dose. If no early PK or safety trends are identified during core team or early SMC monitoring, dosing will continue in participants enrolled during accrual period 1 as per assigned treatment arm.

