
NOTE: Any participants determined to have clearly inadequate RBT concentrations during the accrual period 1 PK evaluation should be monitored closely after dose adjustments for TB outcomes throughout the course of their TB treatment.

After 54-60 accrual period 1 participants have completed 28 days of ART and have drug concentrations available, the core team, together with the SMC, will review the results of the full accrual period 1 interim PK and safety analysis.

If the acceptable PK criteria for RBT and LPV are met, and if three or fewer participants in each treatment arm report  $\geq$  Grade 3 AEs attributed to study-provided drug(s) by 28 days of ART, and if three or fewer participants in each treatment arm discontinue study-provided drug(s) for treatment-limiting toxicity or intolerance (such that PK assessments cannot be completed), then accrual period 2 will open at the planned dose schedules of LPV/r and RBT.

If acceptable PK criteria are not met, or if more than three participants in one or more treatment arms report  $\geq$  Grade 3 AEs attributed to study-provided drug(s) by 28 days of ART, or if more than three participants in one or more treatment arms discontinue study-provided drug(s) for treatment-limiting toxicity or intolerance (such that PK assessments cannot be completed), the SMC, in consultation with the core team, may elect to adjust the doses of RBT and/or LPV/r, as described above for all participants in the affected arm identified with inadequate study-provided drug concentrations. Repeat steady-state (day 12  $\pm$  2 after dose adjustment) drug concentrations will be obtained for only the study arm participants in whom a dose was adjusted. A second accrual period 1 PK and safety interim analysis will be conducted after all accrual period 1 participants undergoing dose adjustment have completed 28 days of dose-adjusted treatment and when day 12  $\pm$  2 post-dose adjustment levels are. This second analysis will include all accrual period 1 participants with available data.

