#### 10.2.4 RBT and LPV Quantitation

RBT and LPV concentrations will be determined in an ACTG CLIA-certified pharmacology laboratory. The goal is for RBT and LPV concentration information from the day  $12 \pm 2$  PK study to be available for evaluation by the A5290 core team during the dose-finding period in accrual period 1 participants. Accrual period 1 participants for whom early dose adjustments are recommended will have drug concentrations repeated  $12 \pm 2$  days after initiating the adjusted dose. If no early PK or safety trends are identified during core team or SMC monitoring, dosing will continue in participants enrolled during accrual period 1 as per assigned treatment arm.

10.3 Primary and Secondary Data, Modeling, and Data Analysis for the Dose-Finding Study in Accrual Period 1 Participants

The observed concentrations of RBT and LPV and the times post dose that these concentrations were obtained will be summarized.

The primary PK characteristics for RBT are:  $C_{max}$ , time to maximum plasma concentration ( $T_{max}$ ), 24-hour post dose plasma concentration ( $C_{24h}$ ), area under the concentration-time curve ( $AUC_{0-24}$ ), and apparent oral clearance (CL/F). Standard noncompartmental techniques will be used to assess PK parameters. The AUC will be determined using the trapezoidal rule.  $C_{max}$  will be taken as the maximum observed concentration.  $T_{max}$  is the time at which  $C_{max}$  occurs. If more than one  $C_{max}$  and  $T_{max}$  occur in a given profile, the median of these values will be taken. The 24-hour post dose concentrations will be the directly measured value. Apparent oral clearance will be calculated as  $CL/F = \text{dose}/AUC_{0-24}$ . The elimination half-life is considered a secondary parameter and will be determined using regression analysis when possible.

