#### 10.4 Anticipated Outcomes for the Dose-Finding Study in Accrual Period 1 Participants

These data will provide guidance to the A5290 core team and SMC prior to the opening of accrual period 2 as to whether the current management approach for the drug-drug interaction between RBT and LPV/r (a RBT dose of 150 mg once daily) produces RBT plasma concentrations comparable to those of RBT 300 mg once daily without LPV/r observed in prior PK studies. Additionally, these accrual period 1 PK evaluations will provide guidance as to whether the management strategy for the drug-drug interaction between LPV/r and RIF (Arm B) of using double-dose LPV/r (i.e., 800/200 mg BID) achieves adequate LPV concentrations.

If the RBT PK data fall outside the effective ranges and the team determines that a dose adjustment is warranted, the team will consider two possibilities – an adjustment to 300 mg TIW as indicated in Table 5.1 or a change to 300 mg daily based on the RBT PK from the accrual period 1 dose-finding period and the assessment of which dose adjustment would best approximate the reference PK parameters for RBT 300 mg once daily given without LPV/r, as described above in section 10.3. If the team determines a RBT dose decrease is warranted, the dose will be reduced to the 150 mg TIW dose currently recommended. No substantive effect of RBT on LPV/r concentrations is expected based on prior PK data with this combination; however, if levels in the ranges noted for Arm B are observed in Arm A or Arm C, then dose adjustments will be the same as for Arm B.

#### 10.5 Population Pharmacokinetic Study Design in Participants Enrolled During Accrual Period 2

##### 10.5.1 Sample Size for Accrual Period 2

411 participants will be randomized 1:1:1 to Arm A, B, or C (or with equal probability to the remaining sample size in the remaining treatment arms) at the doses determined during the dose-finding period in accrual period 1 participants, and with a population PK approach in the accrual period 2.

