#### **1.5 PK and Safety Interim Objectives**

##### **1.5.1 PK Criteria**

- 1) For LPV in Arm B, the primary PK parameter is the day 12 ± 2 (after initiation of study-provided ART and TB medications)  $C_{min}$  ( $C_{12}$ ), and the acceptable lower limit value is  $\geq 1$  mg/L. LPV concentrations in Arm B will be judged acceptable if no more than three participants have a  $C_{min} < 1$  mg/L.
- 2) For RBT (Arms A and C), equivalence analyses will compare day 12 ± 2 (after initiation of study-provided ART and TB medications) RBT 24-hour AUC and  $C_{max}$  with control data derived from prior PK studies, as determined by whether the 90% confidence intervals of the ratios of the RBT concentrations (when co-administered with LPV/r) relative to daily RBT concentrations in the absence of LPV/r are fully contained within the pre-specified NEB of 67%-150%. RBT concentrations in Arms A and C will be judged acceptable if equivalence is declared according to these PK parameters.

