### 5.2.2 Rifabutin (RBT)

- **Note:** The historical controls are Sekar, Ngoc Lan, and Naiker. Only Arms A and C will be included.
- Table summarizing the number of participants excluded from the RBT PK interim analysis with reasons by treatment arm.
- Table summarizing the RBT PK parameters (all available) with sample size, mean, standard deviation, coefficient of variation, median, and quartiles by treatment arm, with Wilcoxon test p-values [PK Study Objective #2; see section 1.6].
- Figure of A5290 and historical control RBT PK parameters ( $AUC$ ,  $C_{max}$ ,  $C_{last}$ ). A5290 data will be pooled over both arms and each historical control will be plotted separately [PK Study Objective #2; see section 1.6].
- Table summarizing the comparison of RBT PK parameters ( $AUC$ ,  $C_{max}$ ,  $C_{last}$ ) to historical controls, with Wilcoxon p-values. A5290 data will be pooled over both arms and each historical control will be tested separately [PK Study Objective #2; see section 1.6].
- Table summarizing the desacetyl RBT PK parameters (all available) with sample size, mean, standard deviation, coefficient of variation, median, and quartiles by treatment arm, with Wilcoxon test p-values [PK Study Objective #2; see section 1.6].
- Figure of A5290 and historical control desRBT PK parameters ( $AUC$ ,  $C_{max}$ ,  $C_{last}$ ). A5290 data will be pooled over both arms and each historical control will be plotted separately [PK Study Objective #2; see section 1.6].
- Table summarizing the comparison of desRBT PK parameters ( $AUC$ ,  $C_{max}$ ,  $C_{last}$ ) to historical controls, with Wilcoxon p-values. A5290 data will be pooled over both arms and each historical control will be tested separately [PK Study Objective #2; see section 1.6].

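### Rifabutin CL/F and dosing-day AUC0-24 are defined for a 24-hour dosing interval and misstate any profile taken on the three-times-weekly doses that Table 5.1 allows

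*Protocol*

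**What the plan says.** Arms A and C take rifabutin 150 mg daily, seven days a week, once ART starts (Protocol 3.0 and 5.1.1). When rifabutin is low, Table 5.1 says "Adjust RBT to RBT 300 mg orally three times weekly (TIW) or 300 mg orally once daily (see section 10.4"; when it is high, the dose falls to 150 mg TIW. For individuals, Cmax "will be used for the purpose of individual dose adjustment for low or high RBT concentrations": below 250 ng/mL is low and above 900 ng/mL is high. Section 10.4 has the team choose between the two increases by "the assessment of which dose adjustment would best approximate the reference PK parameters for RBT 300 mg once daily given without LPV/r".

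Sampling runs from pre-dose to 24 h (10.2.2). Section 10.3 lists CL/F among the primary rifabutin characteristics and fixes one formula: "Apparent oral clearance will be calculated as" dose divided by AUC0-24. No TIW variant is given. The arm-level criterion uses 24-hour AUC and Cmax and passes if the 90% confidence intervals of the ratios "relative to daily RBT concentrations in the absence of LPV/r are fully contained within the pre-specified NEB of 67%-150"% (SAP 1.5.1; likewise Protocol 9.5.1).

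TIW profiles can arise in two ways. Adjusted participants are re-sampled 12 ± 2 days after the change, and an SMC-recommended dose "will be implemented for any new accrual period 1 participants enrolled as soon as possible after the review" (Protocol 9.5.1). Of the second interim analysis, which follows post-adjustment sampling, the protocol says: "This second analysis will include all accrual period 1 participants with available data". It then asks whether the PK criteria are met. SAP 5.2.2 plans a "Table summarizing the RBT PK parameters (all available) with sample size, mean, standard deviation, coefficient of variation, median, and quartiles by treatment arm", with no split by dosing schedule.

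**The concern.** Dose over AUC0-24 is a clearance only when 24 h is the dosing interval. On TIW each dose covers 48 or 72 h, so AUC0-24 leaves out part of what the dose produced and the quotient is too large. For the same reason, a dosing-day AUC0-24 leaves out the lower, undosed days. It therefore reads above the participant's average daily exposure, while the once-daily control has no undosed days to omit.

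The reporting of rifabutin PK is at stake. SAP 1.6 states that accrual period 2 will not open and that the PK objectives are analysed now, so these tables are the trial's rifabutin PK output. An uncorrected TIW profile would suggest faster clearance and more average drug than the participant had. If such values entered the 67%-150% ratio, they would push the AUC part upwards.

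**Working it through.** No sample size or stated probability depends on this point, so there is no plan figure to reproduce. The inputs are the doses in Table 5.1 and the medians that Protocol 2.1 cites from a 16-participant South African study (AUC0-24 in ng·h/mL, Cmax in ng/mL): 300 mg daily without LPV/r, 3026 and 297; 150 mg TIW with LPV/r, 2307 and 168; 150 mg daily with LPV/r, 5010 and 311. Assumptions: linear PK, and 2307 is a dosing-day value.

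**Weekly dose.** 150 × 7 = 1050 mg; 300 × 3 = 900 mg; 900/1050 = 0.857, or -14.3%. The other remedy, 300 mg daily, is 2100 mg (+100%).

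**Cmax.** 2 × 168 = 336; 336/311 = 1.08, or +8%.

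**Clearance by the Section 10.3 formula.** Daily: 150 mg/5010 = 29.9 L/h. TIW: 150 mg/2307 = 65.0 L/h. Ratio 2.17, with the same dose and co-drug.

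**Dosing-day AUC0-24 against average exposure.** Expected daily average on 150 mg TIW: 5010 × 3/7 = 2147; 2307/2147 = 1.074. For 300 mg TIW: 2 × 2307 = 4614 on a dosing day, against an average of 0.857 × 5010 = 4294. The overstatement is 7.4%. Against 150 mg daily, the dosing-day value reads 4614/5010 = 0.921 where the average is 0.857.

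**Dependence on half-life.** The documents give no half-life. Assumed model: one compartment, linear, absorption rate 0.7/h, weekly steady state, doses at 0, 48 and 96 h, mean of the three dosing days. Column 3 is column 2 divided by 0.857; column 4 is (7/3) divided by column 3.

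| Half-life (h) | AUC0-24, 300 mg TIW / 150 mg daily | AUC0-24 / true average | CL/F by formula / true |
|---|---|---|---|
| 12 | 1.535 | 1.79 | 1.30 |
| 24 | 1.228 | 1.43 | 1.63 |
| 36 | 1.105 | 1.29 | 1.81 |
| 72 | 0.979 | 1.14 | 2.04 |
| 135 | 0.921 | 1.07 | 2.17 |

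The cited medians correspond to about 135 h in this model. The shorter half-lives fit them poorly, so 7% is the better-supported figure for AUC.

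**If TIW values entered the equivalence ratio.** Table 9.1 (18 vs 18) implies a confidence-interval factor of 80.1/67.3 = 1.190. The AUC part then passes for an observed ratio between 0.67 × 1.190 = 0.797 and 1.50/1.190 = 1.260. With all 18 on TIW, these edges correspond to true averages of 0.797/1.074 = 0.742 and 1.260/1.074 = 1.173. With 5 of 18 on TIW, the factor is 1.0745^(5/18) = 1.020 and the lower edge is 0.797/1.020 = 0.782. Both counts are illustrations.

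**Choice between remedies by AUC.** Let r be the starting AUC ratio to the reference. The metric changes which remedy is nearer only for r from 2/(2 + 0.921) = 0.685 to 2/(2 + 0.857) = 0.700 on the arithmetic scale, or from √(1/(2 × 0.921)) = 0.737 to √(1/(2 × 0.857)) = 0.764 on the log scale.

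**The case against.** A reader might infer from the 14.3% that 300 mg TIW is a mistaken remedy. The documents do not support that. The individual trigger is Cmax, and TIW raises it. With the cited reference Cmax of 297, TIW (×1.08) comes closer than 300 mg daily (×2) for starting values of about 193 to 250 ng/mL (arithmetic) or 202 to 250 (log), just under the trigger. The daily alternative is also offered, and Section 9.5.1 brings clinical data into dose decisions. A first choice under Section 10.4 would be projected from daily profiles, before any TIW profile existed. All of this stands.

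A reader might also infer that the pass criterion is contaminated. The plan nowhere says that TIW and daily values are pooled, and SAP 1.5.1 times its criterion from the start of study-provided ART and TB medications, which read literally leaves out re-sampled profiles. The text at the opening of SAP Section 5 was not available here and may hold population rules. That limits the claim but does not remove it: Protocol 9.5.1 runs the second analysis with post-adjustment profiles and applies the PK criteria to it, and a new enrollee started on an adjusted dose would have a first profile on TIW.

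It is also fair that CL/F enters no pass criterion, that the SAP objective names AUC, Cmax and Cmin, and that the 7% rests on medians from a small study.

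**Conclusion.** The point holds as a minor analysis correction. The Section 10.3 clearance formula gives a wrong result for both TIW schedules that Table 5.1 prescribes: about 2.2-fold too high on the cited medians, and 1.3- to 2.2-fold over assumed half-lives of 12 to 135 h. Dosing-day AUC0-24 overstates average TIW exposure by about 7% on those medians and by more with a shorter half-life. Both sizes assume linear PK, and the ranges also assume the one-compartment model. The lower weekly dose follows from the doses alone; it is something to weigh under Section 10.4, not an error.

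Nothing here shows that a pass decision or a choice of remedy was or would be wrong. The AUC error changes an AUC-based choice only in narrow ranges, and the equivalence shifts above apply only if TIW values enter the ratio. The reach is accrual period 1 participants in Arms A and C moved to TIW. The documents do not give their number, which may be zero.

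**What to change.** In Protocol 10.3 and 10.4 and SAP 5.1.2 and 5.2.2:

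1. Report TIW rifabutin profiles separately from daily profiles.
2. Keep TIW dosing-day AUC0-24 out of the 67%-150% ratio against the daily control.
3. Compute TIW CL/F as weekly dose over estimated weekly AUC, and omit it where the gap since the previous dose is undocumented. In that case give Cmax and AUC0-24 descriptively, labelled as dosing-day values.
4. State in 10.4 that 300 mg TIW supplies 14.3% less drug per week than 150 mg daily, so that the team weighs it beside Cmax.

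Weekly AUC can be estimated as 3 × AUC0-24 + 3 × AUC24-48 + AUC48-72, taking the decline after 24 h from the 24 h sample and a pre-dose sample drawn after a 48 h gap. In a noise-free check on the planned sampling times, this gave 0.98 to 1.04 of the true weekly average for half-lives of 12 to 135 h. At 135 h it gave 0.98 or 1.02 (second or third dose of the week), against 1.07 or 1.11 uncorrected. Assay and within-person variation would widen this.

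The cost is a short SAP paragraph and a clarification memo, with no extra samples. The drawbacks are extrapolation beyond 24 h, with no samples between 6 and 24 h, and reliance on TB treatment records for the last dose date, because Section 10.2.3 requires dose times only for the PK day and the day before.
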